SYNOPSIS

Sacral Chordoma: a Randomized & Observational study on surgery versus definitive radiation therapy in primary localized disease (SACRO)

Sacral Chordoma: a Randomized & Observational study on surgery versus definitive radiation therapy in primary localized disease (SACRO)

Trial name: SACRO

Study code: ISG -2016-SACRO

Sponsor's Name and Address: Italian Sarcoma Group
c/o Istituti Ortopedici Rizzoli
[name]

Sponsor's [contact]

Sponsor's [contact]

Study Number/Version/Date: Amendment Vers 1.1. 16 November 2020

Type: No Profit

Founding: [Chordoma Foundation](#)

The undersigned confirm that they agree to conduct the study under the conditions described in this protocol

Confidentiality statement: The following confidential information is the property of the Sponsor. As long as the information contained in this protocol has not been published, it may only be used when permission has been obtained from the Sponsor. It is not possible to make reproductions of all or sections of this protocol. Commercial use of the information is only possible with the permission of the proprietor and is subject to a license fee.

SYNOPSIS

SACral Chordoma: a Randomized & Observational study on surgery versus definitive radiation therapy in primary localized disease (SACRO)

SYNOPSIS

Type of Study	International, multicentre, non-pharmacological, comparative, open-label, parallel-group, mixed Observational/Randomized Controlled Trial.
Protocol Code	ISG SACRO
Study Design	
International, multicentre, non-pharmacological, comparative, open-label, parallel-group, mixed Observational-Randomized Controlled Trial.
 
All the patients, who are candidate for the study will receive full information on the characteristics, potential effectiveness and side effects of the two alternatives treatments (radiotherapy and standard surgical treatment \pm RT);
 
Eligible and well-informed patients who give their consent to participate will be asked to choose among 3 alternative treatment options:
 
A. to undergo surgery (\pm RT)
 
B. to undergo definitive radiotherapy
 
C. to be randomized to either definitive radiotherapy or surgery (\pm RT).
 
As reported in the subsequent flow-chart patients who refuse randomization (treatment option c.) will be included in the Prospective Cohort Study (PCS) and will be treated accordingly to their choice (treatment option a. or treatment option b.). The same radiotherapy and surgical regimen will be administered in the PCS and in the Randomized Clinical Trial (RCT).
 
 <pre> graph TD A[Assessed for Eligibility] --> B[Excluded] A --> C[Randomised] A --> D[Allocated to Radiotherapy] A --> E[Allocated to Surgery] C --> F[Allocated to Radiotherapy] C --> G[Allocated to Surgery] D --- H[Prospective Cohort Study] E --- H F --- I[Randomised Controlled Trial] G --- I </pre> 
 
If for country specific regulation or, institutional reasons a site could not participate to both cohorts (Prospective and Randomized), it is allowed to participate only to the Prospective, non-randomized cohort.
 
In this case the Institutional Review Board (IRB)/Independent Ethics Committee (IEC) could approve only the Prospective Cohort Study.”

Sponsor	Italian Sarcoma Group (ISG) [name] www.italiansarcomagroup.org

SYNOPSIS

SACRAL Chordoma: a Randomized & Observational study on surgery versus definitive radiation therapy in primary localized disease (SACRO)

Global Study Coordinators	
Surgery Global Coordinator: Dott. [name] - Fondazione IRCCS Istituto Nazionale dei Tumori, Milano
 
Radiotherapy Global Coordinator: Dott. [name]- CNAO di Pavia

Study Objective	
Primary objective: This study is aimed at estimating the effectiveness of definitive radiotherapy as compared to standard surgical treatment for patients with primary sacral chordoma who are candidates to a complete en-bloc resection, in term of relapse-free-survival (RFS)
 
Secondary objectives: To estimate the efficacy, activity, safety, QoL of definitive radiotherapy as compared to standard surgical treatment for patients with primary sacral chordoma who are candidates to a complete en-bloc resection. To identify patients, radiological and pathological characteristics that might be used as predictors of relapse-free survival (RFS)/ progression free survival (PFS), overall survival (OS) To identify patients, radiological and pathological characteristics that might be used as predictors of treatment effects
 
Primary endpoint
 
 - The RFS, defined for each patient as the time from randomization (RCT) or treatment start date (PCS) to the date of local disease relapse, distant disease relapse, second primary malignancy or death from any cause, whichever occurred first. For patients treated with definitive radiotherapy not achieving CR as well as patients in R1/R2 after surgery not achieving a CR after post-operative radiotherapy the event for the RFS is the disease progression instead of the disease relapse. . 
Subjects not relapsed or died at the time of the analysis will be censored at the last disease assessment date. Disease relapse/progression will be determined radiologically for any appearance of new malignant lesion/s or dimensional increase of any size of malignant lesion/s already present at the baseline assessment.
 
Secondary endpoints
 
- Efficacy endpoints
 
 - Overall Survival (OS), defined for each patient as the time from randomization (RCT) or treatment start date (PCS) to the date of death from any cause. Subjects alive at the time of the analysis will be censored at the date of last contact. - Survival Post Progression (SPP), defined for each patient as the time from local disease relapse, distant disease relapse or second primary malignancy, whichever occurred first, to the date of death from any cause. SPP is equal to 0 in case of death before disease relapse. For patients treated with Radiotherapy not achieving CR as well as patients in R1/R2 after surgery not achieving a CR after Radiotherapy the starting point for the SPP is the local disease progression instead of the local disease relapse. 
- Activity endpoints
 
 - The Local Relapse Failure (LRF), defined for each patient as the time from randomization (RCT) or treatment start date (PCS) to the date of local disease relapse. Distant relapse, second primary malignancy or death before local disease relapse will be considered competing events; subjects alive and not relapsed at the time of the analysis will be censored at the last disease assessment date. Disease relapse will be determined radiologically for any appearance of new malignant lesion/s or dimensional increase of malignant lesion/s already present at the baseline assessment. For patients treated with Radiotherapy not achieving CR as well as patients in R1/R2 after surgery not achieving a CR after Radiotherapy the event for the LRF is the local disease progression instead of the local disease relapse.

SYNOPSIS

SACRAL Chordoma: a Randomized & Observational study on surgery versus definitive radiation therapy in primary localized disease (SACRO)

	
 - The Distant Relapse Failure (DRF), defined for each patient as the time from randomization (RCT) or treatment start date (PCS) to the date of distant disease relapse. Local relapse, second primary malignancy or death before any distant disease relapse will be considered competing events; subjects alive and not relapsed at the time of the analysis will be censored at the last disease assessment date. Disease relapse will be determined radiologically for any appearance of new malignant lesion/s or dimensional increase of malignant lesion/s already present at the baseline assessment. - Best Response rate to definitive radiotherapy will be evaluated radiologically at end of RT, 3 months, 6 months and 12 months after radiotherapy - Time to best response rate to definitive radiotherapy will be evaluated radiologically at end of RT, 3 months, 6 months and 12 months after radiotherapy. 
- Safety endpoints
 
 - Incidence, nature, severity and seriousness of AEs, according to NCI-CTCAE, version 4.0 (see Appendix 2) - Maximum toxicity grade experienced by each patient for each specific toxicity - Percentage of patients experiencing grade 3-4 toxicity for each specific toxicity - Patients with at least a SAE - Patients with at least a suspect unexpected serious adverse reaction (SUSAR) - Adverse events will be evaluated using the NCI-CTCAE scale, version 4.0 - Post-operative morbidity evaluated according to Clavien-Dindo scale - Neurological impairment evaluated according to CTC-AE scale (version 4.0) - 
- Quality of life (QoL) endpoints
 
 - Maximum grade experienced by each patient for each specific item - Maximum grade experienced by each patient for each specific dimension associated with QoL (e.g. functional ability, emotional well-being, sexuality/intimacy, family well-being, treatment satisfaction, and social functioning) - Average grade experienced by each patient for each specific item - Average grade experienced by each patient for each specific dimension associated with QoL (e.g. functional ability, emotional well-being, sexuality/intimacy, family well-being, treatment satisfaction, and social functioning) 
Quality of Life will be assessed through validated evaluation scale

Disease Study	Localized sacral chordoma
Target Population	Patients with a primary and localized sacral chordoma amenable to complete surgical resection and definitive radiotherapy.
Sample Size	
All patients who met the enrollment criteria will constitute the study population that will be splitted in two cohorts according to the choice of each patient. The PCS population will include all patients, who refused randomization and started A. or B. treatment options. The RCT population will include all the enrolled patients who agreed to randomization and were randomized in the RCT study.
 
The safety-QoL population will include all the enrolled patients in both cohort who received option A or B.
 
Recruitment into the RCT will continue until the estimates have become sufficiently stable or extreme to allow a clinical decision in most patients, as indicated by the increasing rate of refusals to accept randomization; recruitment into the PCS will continue until new, more promising or less devastating therapies become available.

SYNOPSIS

SACRAL Chordoma: a Randomized & Observational study on surgery versus definitive radiation therapy in primary localized disease (SACRO)

	The study will be closed when all the enrolled patients will have completed the study treatment; the database lock and the last and definitive statistical analysis will be done approximately one year after the last patient has been enrolled.
Treatments	Definitive radiotherapy (adron therapy, carbon ion radiotherapy or proton therapy) as compared to standard surgical treatment.
Inclusion Criteria	
 1. Histologically confirmed diagnosis (brachyury expression) of primary sacral chordoma, of any diameter and arising at any site from S1 to coccyx. 2. Age \geq 18 years 3. ECOG-performance status (PS) 0-2 (Appendix 5) 4. No previous antineoplastic therapy 5. Macroscopic tumor detectable at MRI/CT scan 6. Patient amenable for surgery 7. Patient amenable for RT
Exclusion Criteria	
 1. Distant metastasis (M+) 2. Inability to maintain treatment position 3. Prior radiotherapy to the pelvic region 4. Prior therapy for sacral chordoma (including surgery, cryoablation, hyperthermia, etc) 5. Local conditions that increase the risk of RT toxicity (tumor ulcerated skin infiltration, non-healing soft tissue infection, fistula in treatment field) 6. Rectal wall infiltration 7. General conditions that increase the risk of RT toxicity (active sclerodermia, xeroderma pigmentosum, cutaneous porphyria) 8. Presence of a second active cancer (with the exception of non-melanoma skin cancer in-situ cervix neoplasia and other in-situ neoplasia) 9. Severe comorbidities resulting in a prognosis of less than 6 months 10. Inability to give informed consent 11. Other malignancy within the last 5 years 12. Performance status \geq 2 (ECOG). 13. Significant cardiovascular disease (for example, dyspnea > 2 NYHA) 14. Significant systemic diseases grade \geq 3 on the NCI-CTCAE v4.03 scale, that limit patient availability, or according to investigator judgment may contribute significantly to treatment toxicity 15. Women who are pregnant or breast-feeding - Women of childbearing potential must have a negative pregnancy test performed within 7 days before the start of treatment. Postmenopausal is defined as: 
 - Amenorrheic for 1 year or more following cessation of exogenous hormonal treatments - LH and FSH levels in the post menopausal range for women under 50 - Radiation-induced oophorectomy with last menses >1 year ago - Chemotherapy-induced menopause with >1 year interval since last menses - Surgical sterilisation (bilateral oophorectomy or hysterectomy) 16. Psychological, familial, social or geographic circumstances that limit the patient's ability to comply with the protocol or informed consent

SYNOPSIS

SACRAL Chordoma: a Randomized & Observational study on surgery versus definitive radiation therapy in primary localized disease (SACRO)

Statistical methods	This study is designed following a Bayesian statistical approach; the final objective of the bayesian statistical analysis will be to estimate a posterior probability distribution of the relative efficacy of the 2 treatment strategies being compared. To this aim, two independent, but sequential analyses are planned; the 1st one will be carried out on the PCS population (Learning data analysis) and the 2nd on the RCT population (Primary data analysis).
----------------------------	---

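### The PCS starts the clock at treatment start and counts only starters, while the RCT counts everyone from randomisation, so the same endpoint names stand for different quantities in the two cohorts

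*Protocol*

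**What the plan says.** All references are to the protocol Synopsis.

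- **Time origin (Study Objective).** The primary endpoint reads "The RFS, defined for each patient as the time from randomization (RCT) or treatment start date (PCS"). The secondary endpoints repeat the split: "Overall Survival (OS), defined for each patient as the time from randomization (RCT) or treatment start date (PCS"), "The Local Relapse Failure (LRF), defined for each patient as the time from randomization (RCT) or treatment start date (PCS") and "The Distant Relapse Failure (DRF), defined for each patient as the time from randomization (RCT) or treatment start date (PCS").
- **Populations (Sample Size).** For the cohort: "The PCS population will include all patients, who refused randomization and started A. or B. treatment options". For the trial: "The RCT population will include all the enrolled patients who agreed to randomization and were randomized in the RCT study". Safety and QoL have a population of their own, made up of treated patients from both cohorts.
- **Entry (Study Design).** Patients consent and then choose surgery, definitive radiotherapy or randomisation; "patients who refuse randomization (treatment option c.) will be included in the Prospective Cohort Study (PCS") and are treated as they chose. The choice therefore comes before treatment.
- **Use (Statistical methods).** The aim is a single posterior for how the two strategies compare in efficacy. Of the two analyses planned to that end, "the 1st one will be carried out on the PCS population (Learning data analysis) and the 2nd on the RCT population (Primary data analysis"). The section calls them independent and also sequential.

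**The concern.** The RCT is anchored at assignment: everyone randomised, from randomisation, treated or not. The PCS is anchored at treatment: only those who reached it, from the day it began. The RCT thus measures the outcome of a strategy from the moment it is assigned; the PCS measures the outcome of patients who got as far as starting.

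The comparison is of strategies, and waits for an operation and for a radiotherapy slot need not be equal. If pre-treatment failures differ between the options, the RCT contrast includes that difference and the PCS contrast leaves it out. Disagreement between the learning and primary results could then come from the definitions rather than from patients or treatments, and the reader could not tell which.

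**Working it through.** The protocol states no sample size, event rate, waiting time or non-start rate, so it has no figure to reproduce. The first step compares definitions. The other steps show scale, and all their inputs are assumptions.

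**1. What happens to a failure between choice (or randomisation) and treatment start**

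| Occurrence before treatment | RCT | PCS |
|---|---|---|
| Death | RFS and OS event; competing event for LRF and DRF | Patient is not in the population |
| Distant relapse | RFS and DRF event; competing event for LRF | Falls before time zero; patient excluded if treatment never starts |
| Second primary malignancy | RFS event; competing event for LRF and DRF | As for distant relapse |
| Local growth of the untreated tumour | Unclear: progression replaces relapse only for patients already treated | As for distant relapse |
| Becomes unresectable, or changes mind | Stays in; not an event in itself | Excluded if treatment never starts |

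The first three rows establish the mismatch.

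**2. Selection on starting, with equal RFS from choice**

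Let S be 2-year RFS from choice, p the fraction who never start, and f the share of non-starters who fail by 2 years. Ignoring the small shift of origin:

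RFS among starters = (S − p(1 − f)) / (1 − p).

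Assume S = 0.80 under both options.

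- p = 0.02: (0.80 − 0.01)/0.98 = 0.806 at f = 0.5; 0.80/0.98 = 0.816 at f = 1.
- p = 0.08: (0.80 − 0.04)/0.92 = 0.826 at f = 0.5; 0.80/0.92 = 0.870 at f = 1.
- With 2% (surgery) versus 8% (radiotherapy), the gap among starters is 2.0 to 5.3 points. The ratio ln(S radiotherapy)/ln(S surgery) is 0.89 to 0.69.
- With 3% versus 5%: 0.809 versus 0.816 at f = 0.5, and 0.825 versus 0.842 at f = 1. The gap is 0.7 to 1.7 points, the ratio 0.96 to 0.89.
- Swapping the rates reverses the direction. Equal p and f leave no gap and move only the absolute rates.
- At f = 0.20 the formula returns 0.80 for any p, so there is no inflation. Below that, starters look worse: p = 0.08 and f = 0 give 0.72/0.92 = 0.783.

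**3. Equal hazards after treatment**

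Assume the same post-treatment hazard h1 in both arms, a pre-treatment hazard h0 of 1 to 3 times h1, 5-year RFS after treatment of 50 to 70%, 1:1 arms and 5 years of follow-up. With wait w:

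RFS at 5 years from randomisation = exp(−h0·w − h1·(5 − w)).

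Example: 5-year RFS 60% gives h1 = −ln(0.60)/5 = 0.102 per year; take h0 = 2·h1 = 0.204.

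- A 3-month wait loses 1 − exp(−0.204 × 0.25) = 5.0% before treatment. RFS from randomisation is 58.5%, against 60% from treatment start.
- A 1-month wait loses 1.7%, and RFS from randomisation is 59.5%.

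Over the full range:

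| Waits, surgery / radiotherapy | Pre-treatment hazard | HR (radiotherapy v surgery), starters from treatment start | HR, all from randomisation |
|---|---|---|---|
| Equal (1 / 1 month) | 1–3 × | 1.00 | 1.00 |
| Any studied | 1 × | 1.00 | 1.00 |
| 1 / 3 months | 2–3 × | 1.00 | 1.04–1.09 |
| 3 / 1 months | 2–3 × | 1.00 | 0.92–0.96 |
| 1 / 6 months | 2–3 × | 1.00 | 1.10–1.22 |

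Patients lost before treatment are 0.6 to 3.4% for a 1-month wait, 1.8 to 9.9% for 3 months and 3.5 to 18.8% for 6 months. RFS at 5 years is 0 to 6.5 points lower from randomisation than from treatment start.

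**4. Reading the two models together**

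Step 2 holds the choice-anchored effect at null and the starters-only contrast moves. Step 3 holds the post-treatment effect at null and the randomisation-anchored contrast moves. Both show that the two definitions can give different answers for the same patients. Neither shows that the PCS contrast is biased in itself; that depends on which effect is the target.

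**The case against.** Treatment start is a familiar origin for an observational cohort. Both PCS groups share it, so there is no immortal time within the cohort, and a pure shift of origin under constant hazards leaves the hazard ratio unchanged. If the target is the effect among patients who reach treatment, the PCS definition answers it correctly, as step 3 shows. The exclusion criteria remove metastatic disease, comorbidity with a prognosis under 6 months and serious systemic disease, so early failures may be few. All of this stands, and it limits the size of the point. It does not make the two cohorts estimate the same quantity.

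Four stronger readings are tempting, but the protocol does not support them:

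- **Every patient who drops out before treatment is a failure in the RCT.** Becoming unresectable or changing one's mind is not an RFS event, and local growth before treatment is ambiguous.
- **Sample Size flatly contradicts Study Design on who is in the PCS.** Study Design can be read as describing enrolment and Sample Size as defining a narrower analysis set. How to group a patient who chose one option and started the other is a detail a SAP, not shown here, could settle.
- **PCS rates are inflated in all cases.** Step 2 shows that this requires non-starters to fail more often than starters.
- **The mismatch passes straight into the primary result.** Statistical methods calls the analyses independent as well as sequential, and does not say how PCS results enter the RCT posterior.

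**Conclusion.** The point holds as a mismatch of definitions, and that part is certain because the protocol itself fixes both clock and population. A death, distant relapse or second primary between choice and treatment start counts in the RCT and cannot count in the PCS, so the learning and primary analyses estimate different quantities although both serve one posterior on the two strategies.

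The consequences are conditional. PCS absolute rates are too favourable relative to the RCT if non-starters fail more often than starters. The PCS contrast departs from the assignment-anchored one if pre-start failure differs by option. Size and direction cannot be found from the protocol. The assumed cases run from no difference to 5.3 points in 2-year RFS (step 2), and from HR 1.00 to 0.92 or 1.22 (step 3). The upper end needs very unequal non-start or waits combined with high failure before treatment; with short or similar waits the effect is small. This should be changed because the remedy is cheap, not because a large distortion has been shown.

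**What to change.** 1. In the RFS, OS, LRF and DRF definitions, start the PCS clock at the date of consent and choice of A or B, the natural counterpart of randomisation.
2. Define the PCS efficacy population as all eligible consenting patients who chose A or B, grouped by the option chosen, whether or not treatment started. This also settles the group of anyone who switches before starting.
3. Keep the present definition (starters only, from treatment start) as a sensitivity analysis, and keep the treated set for safety and QoL.

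The cost is a change of wording and one date that exists at enrolment. The downside is slight dilution of the PCS contrast by never-treated or switched patients, as already happens in the RCT. Clinical management is not affected.

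### The primary RFS event counts any growth of a baseline lesion, with no allowance for measurement error and no clear reference scan, and this bears unequally on the two arms

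*Protocol*

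**What the plan says.** All references are to the protocol synopsis.

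- **Primary endpoint (Study Objective).** Relapse or progression is determined radiologically, either by a new malignant lesion or by a "dimensional increase of any size of malignant lesion/s already present at the baseline assessment".
- **Who is judged on progression.** Two groups are named: "For patients treated with definitive radiotherapy not achieving CR as well as patients in R1/R2 after surgery not achieving a CR after post-operative radiotherapy". In both groups progression takes the place of relapse as the RFS event.
- **Local and distant relapse failure (LRF, DRF).** The matching sentence reads "dimensional increase of malignant lesion/s already present at the baseline assessment", without the any-size qualifier. Survival post progression (SPP) has no size wording of its own.
- **Entry.** The inclusion criteria require "Macroscopic tumor detectable at MRI/CT scan" and admit tumours of any diameter, so every patient starts with a visible mass.
- **Imaging times.** The only ones given are for response to definitive radiotherapy: "evaluated radiologically at end of RT, 3 months, 6 months and 12 months after radiotherapy". No relapse-assessment schedule appears in the text at hand.
- **Final analysis.** Database lock is about one year after the last enrolment.

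**The concern.** Two scans of an unchanged mass rarely give exactly the same size. With a threshold of zero, any upward difference is a primary event. The error needs a lesion that is still there to be measured. That is the situation after definitive radiotherapy without CR, and it is not the situation after complete resection. Exposure to false events therefore follows treatment allocation, and randomisation does not remove it.

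The reference scan is a second weakness. The words about presence at baseline may name the scan against which growth is judged, or may only separate existing lesions from new ones. The two readings lead to different event dates on the same images.

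At stake is the estimate of relative efficacy. The same RFS definition serves both the cohort (learning) analysis and the randomised (primary) analysis, and recruitment to the randomised part stops once the estimates are sufficiently stable or extreme.

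**Working it through.** The protocol gives no number of events, sample size or measurement error, so there is no stated figure to reproduce. The check asks what the rule does when followed literally.

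**Inputs from the protocol:** zero threshold; four scans after definitive radiotherapy (end of RT, 3, 6 and 12 months), taken from the response endpoints; tumours of any diameter.

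**Assumptions, not in the protocol:** 70 mm lesion (30 mm as the small case), readings rounded to 1 mm, independent normal errors with SD 1, 2 or 3 mm, shrinkage linear over the four scans.

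**1. Stable mass, baseline as reference, exact result.** One baseline and k follow-up readings are exchangeable. No false event occurs only if baseline is the largest of the k + 1 readings, which has probability 1/(k + 1). So P(at least one false event) = k/(k + 1). For k = 1, 2, 3, 4 this is 50%, 67%, 75% and 80%, whatever the size of a continuous error. Rounding creates ties and lowers it somewhat.

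**2. Simulation, 70 mm, four scans, any increase over baseline:**

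| True course | SD 1 mm | SD 2 mm | SD 3 mm |
|---|---|---|---|
| Stable | 66% | 74% | 76% |
| Shrinks 10% | 6% | 25% | 39% |
| Shrinks 30% | 0% | 2% | 9% |

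**3. Effect of noise alone on the arm comparison.** Let p be the true 12-month event risk in both arms, f the share of radiotherapy patients who keep a mass, and q the false-event probability. The apparent radiotherapy risk is p + (1 - p) × f × q. Take p = 10% (assumed):

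- f = 25%, q = 6%: 0.10 + 0.90 × 0.25 × 0.06 = 11%.
- f = 75%, q = 76%: 0.10 + 0.90 × 0.75 × 0.76 = 61%.

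The protocol gives neither f nor the distribution of shrinkage, so the range stays this wide.

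**4. Late detection, if baseline is the reference.** After shrinkage s in diameter, the growth from the smallest size needed to regain baseline is 1/(1 - s) - 1. For s = 10%, 20%, 30% and 50% this is 11%, 25%, 43% and 100%. At s = 20%, a 70 mm mass falls to 56 mm and must grow by 14 mm (14/56 = 25%). In volume that is 1.25³ = 1.95-fold. Steps 2 and 4 act in opposite directions on the radiotherapy arm.

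**5. Smallest size as reference, still without a threshold.** A stable mass escapes only if all five readings fall in strictly descending order, with probability 1/5! = 1/120. The false-event probability is 1 - 1/120 = 99%, worse than the 80% in step 1.

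**6. An example threshold: at least 20% and at least 5 mm over the smallest size, stable mass:**

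| Lesion | Error SD | Unconfirmed | Confirmed at next scan |
|---|---|---|---|
| 70 mm | 3 mm | 1.4% | 0.1% |
| 30 mm | 2 mm | 19% | 3% |
| 30 mm | 3 mm | 51% | 16% |

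The example works for a large lesion but not for a small one unless the event is confirmed.

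**The case against.** Several objections have force.

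- **Baseline as reference is an inference.** A reader might infer that the rule measures growth from baseline and so misses true regrowth after shrinkage. The wording does not compel this, because it may only say which lesions count. Even on that reading, regrowth is delayed until it passes the baseline size. It is missed only if the analysis comes first.
- **Direction.** A reader might infer that the endpoint is biased against radiotherapy. Noise does act that way, but late detection acts the other way, and the protocol has no data to weigh them.
- **The false-event rates are illustrative.** They assume independent errors and literal application to every millimetre. The four scans belong to the response endpoints. Applying the stable-mass rate to the whole radiotherapy arm would be too strong, since the protocol itself provides for CR and many masses may shrink. With 30% shrinkage and small error the distortion nearly vanishes.
- **Asymmetry.** R1/R2 patients without CR after post-operative radiotherapy fall under the same rule.
- **Detail for the SAP.** A confirmation rule is often left to the SAP or an imaging manual, so its absence alone is no defect.
- **LRF and SPP.** LRF omits the any-size words and SPP has no size rule, so they do not plainly inherit the problem.

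These points narrow the finding but do not remove it. The zero threshold is written into the primary endpoint, and an SAP that added a margin would contradict the protocol.

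**Conclusion.** The point holds in this form: the primary endpoint sets a zero growth threshold, leaves the reference scan unclear, and exposes the arms unequally to measurement error. For a mass that stays in place the false-event probability runs from about 0% (30% shrinkage, SD 1 mm) to 76% (stable, SD 3 mm), under the assumptions listed in the working and with baseline as reference. The effect on the treatment comparison depends on how many masses persist and how far they shrink, which the protocol does not give. Neither a net direction of bias nor a definite loss of true regrowth is established. The rule should still be changed, because it defines the primary event in both cohorts and no other part of the text at hand corrects it.

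**What to change.** **Change the primary endpoint wording:**

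1. Replace the any-size rule with a stated minimum increase beyond measurement error that works for small as well as large lesions. The 20% and 5 mm rule is one example, with the small-lesion limits shown in the working.
2. Name one reference scan. For R1/R2 patients, use a post-operative scan. Do not name the smallest size as reference without also setting a threshold, since that makes the noise worse.
3. Require the increase to persist at the next scheduled scan, and date the event at the first.
4. State how suspected events still unconfirmed at database lock are counted.
5. Use the same wording for RFS, LRF, DRF and the start of SPP in both cohorts.
6. Keep the any-size rule as a sensitivity analysis.

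**Cost:** protocol wording and a case report form field for the reference size. No extra scans are needed, because confirmation uses the next scheduled one. Some events become known one visit later, and some will be unconfirmed at the lock about one year after last enrolment, which is why item 4 is needed.
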